Study Day (\pm days)/ Visit	Day 1/ Visit 1	Day 28 (\pm 3)/ Visit 2	Day 56 (\pm 5)/ Visit 3	Day 84 (\pm 5)/ Visit 4	Day 112 (\pm 5)/ Visit 5	Day 140 (\pm 5)/ Visit 6	Day 168 (\pm 5)/ Visit 7	Day 182 (\pm 5)/ Visit 8
Consent/Assent Refer to Section 6.1	X							
Inclusion/Exclusion criteria Refer to Sections 5.1 and 5.2	X							
Demographics Refer to Section 6.2	X ^a							
Height/Weight Refer to Section 6.5	X ^a							
Abbreviated Physical Examination Refer to Section 6.4	X ^b	X					X	X
Medical/Medication History Refer to Section 6.3	X ^b							
Vital Signs Refer to Section 6.7	X ^b	X	X	X	X	X	X	X
HDSM-Ax and HDSM-Ax, Child Refer to Section 6.8	X ^a	X	X	X	X	X	X	X
PGI-S Refer to Section 6.10	X ^{a,b}	X	X	X	X	X	X	X
PGI-C Refer to Section 6.11				X			X	
Safety laboratory testing Refer to Section 6.12.4.2	X ^{a,b}	X					X	X ^d
Pregnancy testing (females only) Refer to Section 6.12.4.1	X ^b	X	X	X	X	X	X	

Description	Screening/ Enrollment	Treatment					End of Treatment/Early Termination	End of Study
		Week 0	Week 4	Week 8	Week 12	Week 16		
Study Day (\pm days)/ Visit	Day 1/ Visit 1	Day 28 (\pm 3)/ Visit 2	Day 56 (\pm 5)/ Visit 3	Day 84 (\pm 5)/ Visit 4	Day 112 (\pm 5)/ Visit 5	Day 140 (\pm 5)/ Visit 6	Day 168 (\pm 5)/ Visit 7	Day 182 (\pm 5)/ Visit 8
Pharmacokinetic sampling Refer to Section 6.12.5	X ^b	X ^c					X ^c	
12-lead ECG Refer to Section 6.8	X ^b	X					X	X ^d
Concomitant Medications Refer to Section 6.13	X ^b	X	X	X	X	X	X	X
AE Assessment Refer to Section 10	X ^b	X	X	X	X	X	X	X
Application Site Tolerability Assessment Refer to Section 6.6	X ^b	X	X	X	X	X	X	
Dosing Refer to Sections 8.4 and 8.5 and Study drug application and dosing diary card completion Refer to Appendix C								
Compliance Refer to Section 8.5	X ^b	X	X	X	X	X	X	
Study Drug Dispensing Refer to Section 8.3	X	X	X	X	X	X		

^a Baseline data (prior to first dose) collected under BBI-4000-CL-105 will be carried over to the current study.

^b Data collected at End of Treatment (Day 8 [\pm 1 day]) under BBI-4000-CL-105 will be carried over to the current study.

^c Collection \geq 12 hours from evening application of drug.

^d Only collect if abnormal at Visit 7/Early Termination Visit.

TABLE OF CONTENTS

AGREEMENT OF INVESTIGATOR COMPLIANCE	3
ABBREVIATIONS	4
PROTOCOL SYNOPSIS	6
SCHEDULE OF ACTIVITIES.....	12
1 INTRODUCTION	18
1.1 Background	18
1.2 Rationale.....	18
1.3 Risk / Benefit Assessment.....	18
3 STUDY OBJECTIVES AND ENDPOINTS	18
3.1 Objectives	18
3.1.1 Primary Objectives	18

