Vital signs, review of concomitant medications, assessment of AEs, completion of patient-reported outcomes (HDSM-Ax or HDSM-Ax, Child, and PGI-S), and urine pregnancy tests (UPT) for all females will be done each visit. Application site tolerability will be assessed at all visits through the end of treatment (EOT) at Week 24 (Day 168 [\pm 5 days]). Blood and urine for safety testing will be collected and analyzed at Week 4 (Day 28 [\pm 3 days]) and Week 24 (Day 168 [\pm 5 days]) for routine hematology, chemistry, and urinalysis parameters. ECGs will be assessed at Week 0 (pre-dose, Day 1), Week 4 (Day 28 [\pm 3 days]), and Week 24 (Day 168 [\pm 5 days]). A PK sample will also be collected at Week 4 (Day 28 [\pm 3 days]) and at Week 24 (Day 168 [\pm 5 days]). At Week 12 (Day [84 \pm 5 days]) and at the end of treatment at Week 24 (Day [162 \pm 5 days]), the subject will also complete the PGI-C. A final visit will be conducted 2 weeks after the last application of study drug. Clinically significant abnormal laboratory parameters, and abnormal ECG noted at the previous visit, should be repeated at this visit. Comfort measures (e.g., topical analgesics and mechanical interference devices) may be used during all study blood collection events to reduce subject discomfort.

A total of 8 scheduled visits will take place over approximately 26 weeks: Week 0 (Day 1), Week 4 (Day 28 [\pm 3 days]), Week 8 (Day 56 [\pm 5 days]), Week 12 (Day 84 [\pm 5 days]), Week 16 (Day 112 [\pm 5 days]), Week 20 (Day 140 [\pm 5 days]), Week 24 (Day 168 [\pm 5 days]), and Week 26 (Day [182 \pm 5 days]). Subjects who prematurely discontinue study drug will complete the EOT (Week 24/Visit 7) visit.

An internal Study Review Committee (SRC), comprising the Sponsor Medical Monitor, Lead Investigator and Contract Research Organization (CRO) Medical Monitor, will facilitate the management and identification of potential safety concerns, will assess whether revisions to the study protocol and/or consent are required, and will evaluate the overall progress of the study.

Figure 1 Study Schematic

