4.5.1 Criteria for Premature Discontinuation

4.5.1.1 Discontinuation from Treatment

A subject must be permanently discontinued from the study drug for any of the following reasons:

- The subject becomes pregnant.
- Allergic or adverse reaction to the study drug.
- Clinically significant AE, which in the opinion of the Investigator, or SRC, would put the subject at unnecessary risk if dosing was continued.
- The subject's axillary hyperhidrosis worsens and requires alternative or supplemental medication during the study.

If a subject is discontinued from treatment, he or she should continue to be followed in the study per the [SCHEDULE OF ACTIVITIES](#). If subject refuses to stay in the study, then he or she will be encouraged to complete the Early Termination Visit 7 study procedures.

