6.12.5 Pharmacokinetics

Approximately 2 mL of blood will be collected for PK analysis at Week 0 (Day 1) [per Day 8/Visit 4 of Study BBI-4000-CL-105], Week 4 (Day 28 [± 3 days]) and Week 24 (Day 168 [± 5 days]). Samples will be collected ≥ 12 hours from the time of dosing with study drug. Details regarding collection, processing, shipping and storage of PK samples will be provided in the laboratory reference manual.

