7.3 End of Treatment/Early Termination: Week 24 (Day 168 [± 5 days])

It is estimated that each visit will take approximately 1.5 hours.

- Interview
 - Update medications since last visit
 - Assessment of AEs
- Assessments
 - Obtain and record vital signs
 - Perform an abbreviated physical examination
 - Complete an ECG
 - HDSM-Ax (or HDSM-Ax, Child) and PGI-S assessment (completed by the subject)
 - PGI-C assessed
 - Application site (axillae) tolerability assessment (completed by subject prior to Investigator assessment, and Investigator assessment)
- Review dosing diary card (compliance check)
- Sample Collection
 - Collect blood sample for safety laboratory testing and PK and urine sample for urine laboratory testing
 - Collect urine sample for pregnancy testing
- Instructions
 - Collect subject's previously dispensed sofrironium bromide gel, 15%, pump container from prior visit. Record weight of container with cap.
 - Collect subject's completed dosing diary card from prior visit and review for compliance.
 - The next visit will be scheduled.

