APPENDIX C STUDY DRUG APPLICATION AND SUBJECT INSTRUCTIONS AND DOSING DIARY CARD

- The study drug will be applied every day, at home before bed, at about the same time.
- The study drug will be applied as follows:

Steps

1. Expose the underarm areas and ensure they are dry. Do not wash the underarm areas for at least 30 minutes prior to application.
2. If caregiver will be applying the gel, gloves (provided) should be worn while dispensing the gel and when washing applicator.
3. Hold the plastic applicator between the index and middle fingers and the thumb of the left hand. Carefully, by applying consistent pressure to the actuator with an index finger, dispense the gel of ONE FULL actuation onto the dome of the white plastic applicator.
4. Immediately apply study drug to the right underarm area.
5. Distribute all the gel expressed using the plastic applicator in a way that covers all the underarm area by gently applying a layer of the product.
6. Repeat steps 3, 4 and 5 for the left underarm. If self-applying use the right hand.
7. Wash both hands and the plastic applicator thoroughly for about 2 minutes.
8. Allow the study drug to dry for 5 minutes before putting any clothes on the upper body.
9. Record in the dosing diary card each time (date and time) the study drug is applied and check off that it was applied to the right and left underarm.

Important information:

- Avoid touching the underarm.
- Subjects should maintain their underarm areas grooming habits but should not shower, shave, or wash the underarm area for at least 8 hours after study product application. If the subject takes a shower, shaves or washes the underarm area in the morning then it should be at least 30 minutes before study product application. Ensure the underarm areas are dry prior to application of the study product.
- Subjects should not apply any other product to the axillary area (including deodorant) for at least 8 hours after study product application.
- The subject/caregiver should use the applicator provided to avoid contact with skin of the hands. Gloves will be provided and should be worn if gel applied by the caregiver. Special care should be taken to avoid contact of the gel with the eyes or mouth. Of note, hands should be washed after applying the gel to avoid possible skin and eye contact with the gel.

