- The study product contains alcohol and is flammable. The subject/caregiver should avoid fire, flames or smoking during the application and until the gel has dried. The subject should not expose the container to fire, flames or extreme heat.

SUBJECT/CAREGIVER INSTRUCTIONS

Please follow these instructions carefully. If you do not understand anything in these instructions, ask the study doctor for help. To contact the study staff, call the telephone number noted below if you have any questions:

Contact: _____ At: _____

If you/your child participates in this study, you/your child will be expected to:

- Follow the instructions that are given and come to the study center for visits with the study doctor or study staff or allow a visiting nurse to come to your/your child's home or school to complete the study visit.
- Record in the dosing diary card each time (date and time) the study drug is applied. Check off that the study drug was applied to your/your child's right and left underarm.
- DO NOT apply the study drug before a study visit (or when the study nurse will be visiting).
- Tell the study doctor or study staff about any changes in your/your child's health or the way you/your child are feeling.
- Tell the study doctor or study staff if you/your child want to stop being in the study at any time.
- Do not shower, shave, or wash the underarm area within 30 minutes of study drug application and for at least 8 hours after study drug application.
- Be careful not to touch the eyes or mouth with the gel or with your hands while applying the gel.
- You/your child must practice the required method of birth control throughout the entire study if you/your child are able to become pregnant.
- You/your child must not breastfeed while you/your child are in the study (for applicable females).
- Use a loose T-shirt or similar clothing item and avoid touching the underarm area.
- Do not start any new medications or change your/your child's medications without approval from the study doctor.
- Do not allow access to the study drug assigned to you/your child to anyone beside the study staff.
- Store the study medications according to the instructions on the label.

IMPORTANT:

- The investigational product contains alcohol and is flammable.
- Avoid fire, flames or smoking during the application and until the gel has dried.
- **Do not** expose the container to fire, flame or extreme heat.

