### **12.3.6 Handling of Actual vs. Planned PK Sampling Timepoints**

Actual post-dose time will be used in the Tables and Listings of individual  $C_{trough}$  values. The PK sample collection window ( $\geq 12$  hrs from previous dose and prior to next dose) will be used to summarize descriptive statistics for  $C_{trough}$  values.

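### SAP 12.3.6 sets no upper time limit for a Ctrough sample once a subject has stopped drug, so off-drug values can enter the Week 24 mean

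*Protocol*

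**What the plan says.** **Sampling time.** Protocol 6.12.5 sets a lower limit only: "Samples will be collected ≥ 12 hours from the time of dosing with study drug". Footnote c of the Schedule of Activities likewise asks for at least 12 "hours from evening application of drug". SAP 12.3.6 is the only place with an upper limit. It summarises Ctrough from samples at least 12 "hrs from previous dose and prior to next dose".

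**Subjects who stop drug.** Protocol 4.1 states: "Subjects who prematurely discontinue study drug will complete the EOT (Week 24/Visit 7) visit". Protocol 4.5.1.1 adds: "If a subject is discontinued from treatment, he or she should continue to be followed in the study per the" Schedule of Activities. The Visit 7 procedures in Protocol 7.3 include: "Collect blood sample for safety laboratory testing and PK and urine sample for urine laboratory testing". The previously dispensed container is collected at that visit and no new one is given out. SAP 12.5 gives Visit 7 the joint label of end of treatment/early termination and Week 24.

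**Analysis.** The PK population needs one quantifiable sample at any time (SAP 12.1). Values below the 0.0555 ng/mL quantification limit count as 0 in the descriptive statistics (SAP 12.3.3). Mean Ctrough is plotted by week to assess exposure, accumulation and steady state (SAP 13.3.2). The primary PK endpoint is Ctrough at Weeks 4 and 24 under 24 weeks of once-daily application (Protocol 3.2.1.2, SAP 7.2.1.2).

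**Subject instructions.** Appendix C tells families "DO NOT apply the study drug before a study visit (or when the study nurse will be visiting". The same appendix says: "The study drug will be applied every day, at home before bed, at about the same time".

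**The concern.** A trough concentration describes the end of a dosing interval during treatment. The SAP's upper limit is an event, the next dose, rather than a number of hours. For a subject who has permanently stopped, that event never comes, and a sample drawn days or months after the last application still fits the definition as written.

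A subject who had a quantifiable value at Week 4, stopped drug, and was then sampled at Week 24 would be in the PK population. That subject could contribute a 0 to the Week 24 mean. The Week 24 point on the plot would then mix exposure on drug with washout. A reader could take the lower mean as absence of accumulation, or as falling exposure in children, when part of the drop only reflects people no longer using the gel.

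The Appendix C line raises a smaller question about the same interval. It gives no hours and no clock time, and the only scheduled dose is at bedtime. A family could therefore wonder whether it refers to the evening before the visit.

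**Working it through.** The plan states no figure to reproduce. All PK analyses are descriptive, and the sample size of up to 24 is carried over from the parent study. The check is a reading of the rules followed by simple arithmetic.

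**1. Can a sample taken off drug satisfy the plan?** Take a subject who permanently stops on Day 28 and is followed on the Schedule to Day 168.
- Time since last dose: (168 − 28) days × 24 h = 3,360 h.
- Lower limit of 12 h: met.
- Upper limit, before the next dose: nothing closes it, because no further dose is planned.
- Visit window, Day 168 ± 5: met.
- PK population: met if any one sample was quantifiable, for example at Week 4.

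The sample therefore enters the Week 24 summary. If it is below 0.0555 ng/mL, it enters as 0.

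**2. Does another rule remove it?**
- Protocol Section 9 lists out-of-window blood samples and dosing errors as violations. A draw that the protocol itself schedules after an authorised discontinuation is neither, so SAP 12.8 is not clearly triggered.
- SAP 12.3.5 allows case-by-case exclusion of values that are erroneous, abnormal or implausible. A low value in someone off drug is none of these.
- SAP 12.3.6 shows actual post-dose times for individual values. That makes the sample visible but does not take it out of the mean.

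**3. Effect on the mean.** Let M be the mean of the on-drug samples, n the number of samples at Week 24, and k the number taken off drug and set to 0.

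Reported mean = M × (n − k)/n, so the relative fall is k/n.

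| n | k (assumed) | (n − k)/n | Fall |
|---|---|---|---|
| 24 | 1 | 23/24 = 0.958 | 4.2% |
| 24 | 2 | 22/24 = 0.917 | 8.3% |
| 24 | 3 | 21/24 = 0.875 | 12.5% |
| 12 | 1 | 11/12 = 0.917 | 8.3% |

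If the off-drug values average a fraction r of M instead of 0, the fall is k(1 − r)/n. For r between 0 and 1, the table therefore gives the largest fall for each k and n.

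**4. Does a limit of 30 h separate the cases?** With once-daily dosing and the 12 h minimum, a sample after the previous evening's dose falls between 12 h and just under 24 h. If that evening is skipped, add 24 h: 36 h to just under 48 h. With assumed clock times (dose 20:00 to 22:00, visit 08:00 to 17:00), the gaps are 10 to 21 h when dosed and 34 to 45 h when skipped. A limit of 30 h falls between the two ranges in both calculations.

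**The case against.** The strongest reply is that a once-daily trough lies by definition within one dosing interval. On that view, the next dose in SAP 12.3.6 means the next scheduled dose, and the endpoint's own reference to 24 weeks of daily application already shuts out someone who stopped at Day 28. Dosing times are imported for the PK analysis, actual times are listed, medians are reported and individual profiles are overlaid, so a washout value would be noticed. Much of this stands: a careful pharmacokineticist would probably handle such a sample sensibly. But the SAP does not state that reading, and after permanent discontinuation there is no scheduled dose for it to refer to. Without a written rule, the choice would be made after the concentrations are known.

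It is also fair to say that the plan does not settle whether an early-termination sample taken well before Day 168 is summarised under Week 24. The clear case is the subject followed to Day 168 itself.

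Three stronger readings are tempting, and the documents do not support them.
- **That Appendix C tells families to skip the previous evening's dose.** Daily bedtime dosing, a diary row for every day with an evening time column, and staff instruction at enrolment all point the other way. The remark about the nurse visiting suggests the visit occasion itself. Skipping is a minority reading.
- **That subjects who complete treatment would routinely be sampled off drug at Week 24.** SAP 13.2 places the final application within the same Day 168 ± 5 window as the visit, and the container stays with the subject until Visit 7.
- **That the bias can be estimated from drug elimination.** No half-life is given, so any such percentage would be invented.

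**Conclusion.** The point holds as a gap in the SAP and is minor. As written, the plan lets samples from subjects who have stopped drug into the Week 24 Ctrough summary, and no rule based on time since last dose takes them out. If those values are below the quantification limit, the direction is clear: Week 24 exposure looks lower than exposure on treatment.

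The size is conditional. One zero among 24 samples lowers the mean by 4.2%, and three lower it by 12.5%. These figures assume the number of off-drug subjects, assume that their results are below 0.0555 ng/mL, and take n at the enrolment ceiling; with fewer samples, each zero weighs more. The documents do not show that any of this is likely. The analysis carries no test or decision rule, so the consequence is a less interpretable mean and plot, not a wrong formal conclusion.

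No Week 4 problem is claimed for subjects on treatment. The Appendix C line is a wording clarification only.

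**What to change.** In SAP 12.3.6, restrict the main Ctrough summary and the weekly mean plot, at every visit including Week 24/early termination, to samples taken from 12 h up to a stated limit after the last documented dose. Show later samples in the listings only, with their actual post-dose time. A limit of about one dosing interval is enough. For example, 30 h is the 24 h interval plus 6 h of slack. The exact figure is a judgement for the pharmacokineticist, since the documents give no PK basis for it; it should be fixed before concentrations are reviewed.

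This costs one sentence. Dose and sampling times are already collected, so it can be done at any time before database lock. The downside is that a few samples leave the summary.

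Secondarily, reword the Appendix C line along these lines: *Apply as usual the evening before the visit; do not apply on the visit day until after the visit.* This changes subject-facing text and needs IRB approval. The SAP change does not depend on it.

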APPENDIX D EXAMPLES OF POTENT INHIBITORS CYP3A AND CYP2D6

Example Potent Inhibitors of CYP3A		
apigenin	hydroxyzine	protease inhibitors
antipsychotics	interferon	ritonavir
candesartan	isoniazid	St. John's Wort (and other herbal supplements)
chloramphenicol	itraconazole	
chlorpheniramine	ketoconazole	
clarithromycin	methoxsalen	sulphaphenazole
cobicistat	mibepradil	telithromycin
cilexetil (cyclohexylcarbonate ester prodrug of candesartan)	miconazole	tripelennamine
	mifepristone	valproic acid
	mometasone furoate	voriconazole
diphenhydramine	montelukast	zafirlukast
felodipine	nefazodone	
gestodene	promethazine	

Example Potent Inhibitors of CYP2D6		
bupropion	fluoxetine	paroxetine
quinidine	terbinafine	

Also refer to FDA reference link “Drug Development and Drug Interactions: Table of Substrates, Inhibitors and Inducers”

[<http://www.fda.gov/Drugs/DevelopmentApprovalProcess/DevelopmentResources/DrugInteractionsLabeling/ucm093664.htm#table2-2>]

Concomitant medication restrictions ([6.13.2](#))

**APPENDIX E EXAMPLES OF POTENT INHIBITORS OF
OCT-2/MATE1/MATE2 TRANSPORTERS**

Example Potent Inhibitors of OCT2		
Cimetidine		

Example Potent Inhibitors of MATE1/MATE2		
Cimetidine	Dolutegravir	Isavuconazole
Ranolazine	Trimethoprim	Vandetanib

Also refer to FDA reference link “Drug Development and Drug Interactions: Table of Substrates, Inhibitors and Inducers”

[<http://www.fda.gov/Drugs/DevelopmentApprovalProcess/DevelopmentResources/DrugInteractionsLabeling/ucm093664.htm#table2-2>]

Prohibited medications (6.13.2)

APPENDIX F APPLICATION SITE TOLERABILITY ASSESSMENTS

These assessments are to be performed for each axilla individually. The designation of “Right Axilla” or “Left Axilla” in the source documents and eCRFs refers to the subject’s right and left axilla respectively in all cases. Subject assessments are to be performed prior to Investigator assessments.

Local Tolerability (Subject): As reported by the Subject to the Investigator, the severity of any symptoms of burning, stinging or itching at the application-site within the previous 24 hours and further any such symptoms persisting longer than 1 hour following study drug application will be described specifically by severity using the following standardized scales:

Score	Burning	Stinging	Itching
0 = Absent	Normal, no discomfort	Normal, no discomfort	Normal, no discomfort
1 = Minimal	An awareness, but no discomfort	An awareness, but no discomfort	An awareness, but no discomfort
2 = Mild	Noticeable discomfort causing intermittent awareness	Noticeable discomfort causing intermittent awareness	Noticeable discomfort causing intermittent awareness
3 = Moderate	Noticeable discomfort causing continuous awareness	Noticeable discomfort causing continuous awareness	Noticeable discomfort causing continuous awareness
4 = Severe	Definite discomfort causing continuous awareness, interfering occasionally with normal daily activities	Definite discomfort causing continuous awareness, interfering occasionally with normal daily activities	Definite discomfort causing continuous awareness, interfering occasionally with normal daily activities

Local tolerability (Investigator): The Investigator will assess the drug-application site for the existence of significant local symptoms. Significant local symptoms are defined as those not ordinarily observed following application of a topical product. The following standardized scales will be used to describe specifically the severity of any erythema or scaling:

Score	Scaling	Erythema
0 = Absent	No scaling	No redness
1 = Minimal	Fine scaling, barely perceptible	Faint red or pink coloration, barely perceptible
2 = Mild	Slight scaling, noticeable only with light scratching	Light red or pink coloration
3 = Moderate	Definitely noticeable scaling	Medium red coloration
4 = Severe	Extensive scaling	Beet red coloration
